Comparison of Local Anesthetic Infusion Pump Versus Depofoam Bupivacaine for Pain Managemen

Date 12/12/2015 ID: 15-1535

Purpose

We propose a randomized controlled study to compare the effectiveness of a localanesthetic continuous infusion pump system versus locally injectable FDA approved DepoFoam bupivacaine (Experal) for postsurgical analgesia in patients undergoing unilateral DIEP free flap reconstruction.

Specific Aims

- Compare the amount of postoperative narcotic use in patients with a localanesthetic continuous infusion pump system, locally injectable liposomal bupivacaine, and a control cohort by recording the type and amount of narcotic use from a patient's medication records.
- 2) Examine the incidence of narcotic-related side effects in the experimental groups as compared to the control cohort by documenting incidents of nausea and vomiting, time to first ambulation, and time to first liquid and solid oral intake.
- 3) Survey patient satisfaction with pain management using a visual analog scale during their hospital stay.

Rationale for the Project

Effective post-surgical pain control in patients undergoing unilateral deep inferior epigastric perforator (DIEP) free flap reconstruction. is critical to patient recovery, and can contribute to faster patient mobilization, shorter hosital stays and reduced health care costs. The admisitration of local anesthetics via wound infiltration is standard of care and an effective practice for postsurgical pain management. However, this method only provides relatively brief analgesia, usually lasting only 12 hours. Other FDA approved delivery systems using an indwelling fusion pump catherter (On–Q pump) are currently being used in our practice and may be used to extend the duration of action of locally adminisisted analgesia by continously infusing anesthetic into the wound. Alternativley, a depot form of bupivicaine has been FDA approved and currently used to deliver a single-dose admistered via wound infiltration for prolonged analgesia by allowing for the diffusion of the drug over an extended period of time. Both of these products are used as standard practice during DIEP free flap reconstructions. However, no studies compare the efficacy of these two methods patients undergoing unilateral DIEP flap reconstructions has been done in a prospective, randomized control manner.

Significance

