Study participants will include non-pregnant women aged 18 years or older scheduled to have unilateral DIEP flap breast reconstruction. Patients will be required to have an ASA physical status classification of 1, 2, or 3. Patients will be excluded if they have a concurrent or recent medical condition that could interfere with study participation, including history of hepatitis, alcohol/substance abuse, uncontrolled psychiatric disorders, known allergy, or contraindication to amide-type local anesthetics, opioids, or propofol. Patients will also be excluded if they have a body weight of less than 50 kg, have participated in another study involving an investigational medication within the prior 30 days, or are taking analgesics (ie, nonsteroidal anti-inflammatory drugs, acetaminophen, or opioids), antidepressants, or glucocorticoids within the 3 days before surgery.

Describe the control population

Group 3 of our study will compromise the control group for our study. Patients in this arm will receive .25% bupivacaine without epinephrine injected using ultrasound guidance in between the internal oblique and transversus abdominis muscles as well as along incisional lines. This form of local wound infiltration is the current standard of care for post-operative pain management for DIEP reconstructions of the breast.

Support the likelihood of recruiting the number of subjects required

Evidence from our Breast Reconstruction database using data transferred from Epic/Clarity, in 2014 show fifty four unilateral DIEP breast reconstructions were performed and in 2013 sixty six unilateral DIEP breast reconstructions were performed.

Project Design and Protocol

All patients meeting the inclusion criteria will be randomized using a blocked randomization technique, stratifying patients by the timing of the procedure, and it will be employed to allocate patients in equal numbers to each group. The randomization will be created using the plan procedure within SAS software (version 9.3 or higher; Cary, NC).. Patients will be assigned to one of three groups: Group 1 -DepoBupivicaine Injection; Group 2- OnQ catheter placement, and the control Group 3- 0.25 % Bupivicaine injection.

Bupivacaine is a commonly utilized medicaiton for post-operative pain control with a favorable side-effect profile. The dosages of medications given in the study are within safe limits.

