The maximum safety dosage of bupivicaine is 2mg/kg with a half life of 3.5 hours. This means a 70kg adult could receive 150mg (.15g). This calculation does not account for the slow release profile of DepoBupivicaine which would increase the maximum safe dose.

The DepoBupivicaine patients (Group 1) will receive an injection of 166mg of DepoBupivicaine diluted in 60mL, the On Q patients (Group 2) will receive an infiltration via an OnQ soaker catheter of 0.25% bupivicaine at 4mL/hour (ie. .01 gram/hour) and 0.25% Bupivicaine patients (Group 3) will receive 2mg/kg of 0.25% of bupivicaine.

Consent

All patients will sign an informed consent that will be presented to them during a preoperative visit with their attending surgeon.

Pre-operative Protocol

No preemptive morphine was given to patients. Patients at high risk for post-operative nausea and vomiting will be given Dexamethasone 4mg and Reglan 10 mg. Anesthesia will be given according to Table 1.

Table 1:

Induction	Propofol	
Intubation (muscle relaxation)	Succinylcholine	
Maintenacnce	Sevoflourane	
Muscle relaxation	Rocuronium	
Analgesia	Fentanyl 2-7 mcg/Kg	
Prophylactic Analgesia	Toradol 30- 60 mg	
Reversal	Glycopirolate + Neostigmine	
Anti-emetic	Zofran 4 mg	

Operative Technique

Surgeons for patients randomized to Group 1(DepoBupivicaine) will be given a schematic for injection of DepoBupivicaine. One 20 cc vial of EXPERAL (266 mg) will be diluted with 60 cc preservative-free normal sterile saline for a total volume of 80 cc. The infiltration technique for the DepoBupivicaine (See Baxter et al, and Hivelin et al) will be 20 cc of injected with a 25-gauge needle on either side of the suture line, (Figure 2 and Figure 3) injected directly into the fascia. The injections will be done in between the internal oblique and transversus abdominus muscles as determined via ultrasound.

Another 20 cc of will be injected on the outside edge of the surgical site where the sensory nerves branch up from the fascia to the skin flap. () The final 20 cc will be injected along the length of the incision where the skin will be anchored down with care to inject the product near the ileoinguinal nerve to ensure appropriate analgesic coverage. Once again, the DepoBupivicaine will be injected directly into the fascia above the muscle layer. All patients will have two closed-suction drains placed at the inferior aspect of the donor site, oriented horizontally and remote from the any infusion catheter..

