Our primary endpoints will be postoperative pain as measured by total postoperative morphine or hydromorphone utilization from a patient controlled anesthesia pump (PCA) and pain scores on visual analog scale (VAS). The VAS will be measured while the patient is at rest (VAS-R) and after the patient is asked to cough (VAS-C). For each patient, the area under the curve (AUC) of the VAS-R will be calculated. Morphine usage will be tracked by patient controlled analgesia (PCA) dispensed. Using the medication chart, any rescue medications beyond the PCA will also be recorded. Patients will be interviewed and asked to rate their postoperative pain on a 10-point scale with 0 being no pain and 10 being the most pain. Another variables recorded will include incidents of nausea or vomiting, time to first ambulation, and time to first liquid and solid oral intake. All measurements for variables were obtained at 6 hrs, 12 hrs, 24 hrs, 48 hrs, 72 hrs. Nursing staff on our designated breast reconstruction floor will be instructed on how to interview patients and collect data for the 6 and 12 hour timepoints. This information will be stored on Epic EMR in a stardard note and nurses will be given a smart text to use in order to appropriately ascertain all information. The 24, 48, and 72 hour time points will be collected by the co-investigators. Any pain medications given by PCA, IV or PO will recorded and converted to morphine as diagramed below:

Drug	Parenteral (mg)	Oral (mg)
Morphine	10	30
Hydromorphone	1.5	7.5
Oxycodone	NA	20
Hydrocodone	NA	30-45
Oxymorphone	1	10
Meperidine	75	300
Codeine	130	200

Equianalgesic Potency Conversion TABLE A

Discuss limitations and difficulties

The limitations of our study include potential confounding pain from the mastectomy site, the subjectivity in patient perception of pain, and differences in patient threshold to request patient- controlled anesthesia and oral narcotics

Provide the tentative schedule for completion

Our schedule for the study will be 6 months continuous enrollment and experimentation from September to February, or until our groups are filled.

Data collection

The data fields will be: Birth date, sex, type of surgery, utilization of mesh, number of mg on PCA, VAS at rest and VAS with cough, number of rescue pain medications given, number of incidents of nausea/vomiting, time to first ambulation, time to first liquid and solid intake post surgery.

Planned Data Analysis

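### The written study-anaesthetic doses contradict each other, and the Group 3 worked example is 25% above the protocol's own 2 mg/kg maximum

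*Combined protocol and SAP*

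**What the plan says.** **Limit.** The Project Design and Protocol section states "The maximum safety dosage of bupivicaine is 2mg/kg with a half life of 3.5 hours" and continues "This means a 70kg adult could receive 150mg (.15g". It adds that this ignores the slow release of the depot product, which would raise the limit for Group 1. The same section asserts: "The dosages of medications given in the study are within safe limits".

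**Group 1.** Project Design and Protocol gives 166 mg with a 60 mL dilution. Operative Technique gives one whole 20 cc vial (266 mg) plus 60 cc saline, for 80 cc in total. It is injected in 20 cc steps: either side of the suture line, the outer edge of the surgical site, and along the incision.

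**Group 2.** 0.25% bupivacaine at 4 mL/h through two catheters, which are removed when the pump is empty. No pump volume is given.

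**Group 3.** 2 mg/kg of 0.25% bupivacaine, illustrated under Operative Technique as 80 cc for an 80 kg patient. The infiltration technique is said to be the same as for Group 1, with the same 20 cc steps.

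**Eligibility.** "Patients will also be excluded if they have a body weight of less than 50 kg".

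**Data.** The Data collection section begins "The data fields will be: Birth date, sex, type of surgery, utilization of mesh, number of mg on PCA", then lists the two pain scores and ends "number of rescue pain medications given, number of incidents of nausea/vomiting, time to first ambulation, time to first liquid and solid intake post surgery". The Post-operative Protocol adds "Any pain medications given by PCA, IV or PO will recorded and converted to morphine as diagramed below". The side-effect aim is "Examine the incidence of narcotic-related side effects in the experimental groups as compared to the control cohort".

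**The concern.** The protocol names a maximum dose, assigns one arm exactly that maximum, and then gives the surgeon a worked example above it. A worked example is what staff tend to follow in theatre, so this is a safety matter as well as a drafting one. The Group 1 conflict leaves open which dose of the depot product the trial is testing.

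The second issue is lesser. The plan has no stated provision for recording how much study anaesthetic each woman received, or for collecting local-anaesthetic toxicity, donor-site or catheter events by arm. The arms differ in these exposures: a depot injection, two indwelling catheters, and a single infiltration. A departure from the intended dose would therefore not show in the planned data, and one method could be preferred on opioid use and pain scores without planned by-arm information on these harms.

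**Working it through.** **Inputs.** Maximum and Group 3 dose 2 mg/kg; 0.25% solution = 2.5 mg/mL; Group 2 rate 4 mL/h; Group 1 as 166 mg or 266 mg (all from Project Design and Protocol or Operative Technique). Entry minimum 50 kg (Subjects in the project).

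**1. The plan's Group 3 example.** Volume = (2 mg/kg × weight) ÷ 2.5 mg/mL = 0.8 mL/kg.
- At 80 kg: 160 mg ÷ 2.5 = 64 mL. The stated 80 cc is not reproduced.
- 80 cc × 2.5 = 200 mg; 200 ÷ 80 = 2.5 mg/kg; 200 ÷ 160 = 1.25, so 25% over.
- 80 cc would equal 160 mg only at 2.0 mg/mL, which is not the stated concentration.

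**2. The 70 kg example.** 2 × 70 = 140 mg. The stated 150 mg is 150 ÷ 70 = 2.14 mg/kg.

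**3. Group 1.** 266 ÷ 166 = 1.60. Using 60 of the 80 mL would deliver 266 × 60 ÷ 80 = 199.5 mg, so part use of the vial does not explain 166 mg.

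**4. Group 2.** 4 × 2.5 = 10 mg/h, which agrees with the stated 0.01 g/h. There is no conflict here.

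**5. The 20 cc steps in Group 3, if fixed at every weight.** They total 20 + 20 + 20 = 60 cc (150 mg), or 2 × 20 + 20 + 20 = 80 cc (200 mg) if 20 cc goes on each side.

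| Weight | Volume at 2 mg/kg | 60 cc gives | 80 cc gives |
|---|---|---|---|
| 50 kg | 40 mL | 3.0 mg/kg | 4.0 mg/kg |
| 70 kg | 56 mL | 2.14 mg/kg | 2.86 mg/kg |
| 80 kg | 64 mL | 1.88 mg/kg | 2.5 mg/kg |
| 100 kg | 80 mL | 1.5 mg/kg | 2.0 mg/kg |

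On this reading the maximum is exceeded below 150 ÷ 2 = 75 kg (60 cc) or 200 ÷ 2 = 100 kg (80 cc).

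**6. What harms data could show.** The plan states no sample size. Assume six months of enrolment at the stated 54 to 66 cases a year, with every case enrolled: 27 to 33 women, or 9 to 11 per arm. With no events, the one-sided 95% upper bound is 1 − 0.05^(1/n): 28% for n = 9 and 24% for n = 11. The schedule also allows enrolment to run until the groups are filled, so these sizes are illustrative.

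**The case against.** **The 20 cc steps may not be fixed.** The text gives the 2 mg/kg rule first, then the 80 kg example, then the steps. Four steps of 20 cc make exactly that example's 80 cc, so they may describe that patient only. This stands. A reader might infer that the protocol prescribes 3.0 or 4.0 mg/kg for a 50 kg woman. Shared technique is compatible with that but does not compel it, and the 2 mg/kg rule itself remains in force. The 25% excess in the worked example does not depend on this reading.

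**The Group 1 volumes may agree.** The 60 mL may be the diluent, matching the 60 cc of saline elsewhere. Then only the milligrams conflict, possibly through a mistyped digit. This also stands, so no conflict in concentration is claimed.

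**Group 1 might seem to break the maximum too.** A reader could set 266 mg against 2 mg/kg. The protocol says slow release raises that limit, so the documents do not support a finding of excess in Group 1.

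**The field list is not exhaustive.** It also omits randomised group, and it omits oral and IV opioid amounts that the Post-operative Protocol says will be recorded. Weight must be known to apply the entry criterion and the dose rule. The sentence on PCA, IV and oral drugs serves opioid conversion, so its silence on local anaesthetic shows little. Absence from the list is therefore weak evidence, and a reader should not infer that harms would go unnoticed or that records will lack the dose. What can be said is that the plan does not provide for extracting and reporting them by arm.

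**Harms are outside the stated aims.** The protocol describes the products as approved and in standard use, and the trial is probably too small to test harms. This is fair, and it is why the data fields are a secondary suggestion.

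**Conclusion.** The doses are wrong as written. Three errors rest on the text and simple arithmetic alone:

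- The Group 3 example gives 200 mg where the rule gives 160 mg, 25% over the protocol's own maximum.
- Group 1 has two doses that differ 1.6-fold.
- The 70 kg maximum is overstated by 10 mg.

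The larger Group 3 excesses, up to 4.0 mg/kg at 50 kg, hold only if the 20 cc steps are fixed at every weight. The documents leave that open, and the ambiguity is itself worth removing. Nothing here shows that any participant received an excess dose.

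The absence of planned by-arm data on anaesthetic given and product-related harms is a gap worth closing cheaply, but it is partly a choice of scope.

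**What to change.** Before enrolment, make four text corrections:

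1. **Group 1:** state one dose in both places. 266 mg in 80 cc fits the whole-vial instruction and four 20 cc injections; the investigators should confirm it.
2. **Group 3 example:** change to 64 mL at 80 kg.
3. **Group 3 technique:** replace the 20 cc steps with a total of 0.8 mL/kg divided equally over the four injection sites (10 mL each at 50 kg, 16 mL each at 80 kg). Uncapped, this passes Group 1's 80 cc above 100 kg; at 120 kg it is 96 mL (240 mg). The investigators should decide on any cap, for example 80 mL, which is reached at 100 kg. Below 100 kg the volume is less than Group 1's, as the 2 mg/kg rule already implies.
4. **70 kg example:** change to 140 mg.

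These cost only editing time.

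As a secondary improvement, add body weight and the mg and mL of study anaesthetic given; for Group 2, add pump start and stop times and volume delivered. Record local-anaesthetic toxicity, donor-site events and, in Group 2, catheter events at the existing assessments up to 72 h, and report them descriptively by arm. The cost is modest extra data entry. Visible catheters mean that recording will not be blind, and numbers will probably be too small to test harms. The toxicity definition and any follow-up beyond 72 h are for the investigators to decide.

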The data will be examined with an analysis of variance (ANOVA) procedure with repeated measures. The design will have one between factor, (group (3), and one within factor, time (6). The analysis will test for a group effect, a time effect and a group by time interaction. We anticipate that the three groups will be comparable at the start. This implies the likelihood of a significant interaction term. If this happens, our primary analysis will focus on the ANOVA for the 72-hour time point. This will show us if a differential effect has occurred. All assumptions of the test will be examined and data transformations or nonparametric methods used if indicated.

We will not be utilizing QHS, rather, one of the plastic surgery residents, [name], will serve as our statistician.

Sample Size Justification

We propose to randomly assign individuals recruited during the recruitment period into 3 equal groups. With three groups this translates to a difference between groups of 5 for total morphine used on day 3 and 0.7 for the VAS. This assumes standard deviations of 4.9 for morphine and 0.7 for VAS. Effects of these sizes represent clinically important differences in the range that we believe will happen.

References:

- Feng LJ. Painless abdominoplasty: the efficacy of combined intercostal and pararectus blocks in reducing postoperative pain and recovery time. Plast Reconstr Surg. 2010 Nov;126(5):1723-32.

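### The repeated-measures ANOVA has no rule for missing readings and no named correction for non-sphericity, so the 72-hour contrast can be biased and the interaction test can exceed 5%

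*Combined protocol and SAP*

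**What the plan says.** Planned Data Analysis sets the method: "The data will be examined with an analysis of variance (ANOVA) procedure with repeated measures". It continues: "The design will have one between factor, (group (3), and one within factor, time (6"). The plan expects a significant group-by-time interaction and then says: "If this happens, our primary analysis will focus on the ANOVA for the 72-hour time point". On assumptions it says: "All assumptions of the test will be examined and data transformations or nonparametric methods used if indicated".

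Post-operative Protocol gives the schedule: "All measurements for variables were obtained at 6 hrs, 12 hrs, 24 hrs, 48 hrs, 72 hrs". That is five times, against six in the analysis section. Opioid use comes from the PCA pump and the medication chart. Specific Aims places the VAS survey within the hospital stay. Rationale for the Project says that effective pain control "can contribute to faster patient mobilization, shorter hosital stays and reduced health care costs".

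The document gives no rule for missing readings, discharge before 72 hours or the analysis set. It names neither sphericity nor an epsilon correction.

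**The concern.** Two separate weaknesses meet in one analysis.

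**Missing readings.** Classical repeated-measures ANOVA needs a full row for each woman, and the 72-hour ANOVA needs a 72-hour value. Both primary endpoints are recorded in hospital. If women with good pain control go home sooner, as the rationale expects, the women absent at 72 hours could differ from those present, and by different amounts in each arm. The pilot described in the protocol points the same way: the arm using less opioid at 72 hours (2.7 against 12.65 mg) was also walking, drinking and eating earlier.

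**Non-sphericity.** The within-patient tests are valid only if differences between all pairs of times have equal variance. Serial readings at 6, 12, 24, 48 and 72 hours will often fail this, because neighbouring readings correlate more than distant ones. The remedies named are "data transformations or nonparametric methods used if indicated". A transformation may even out variances, but neither remedy directly corrects unequal correlations.

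At stake are the size of the 72-hour contrast, the number of women who contribute to it, and the error rate of the test that decides which analysis is primary.

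**Working it through.** The plan states no sample size, alpha, power or missing rate, so it has no figure to reproduce.

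**Inputs from the plan** (Sample Size Justification): morphine difference 5, SD 4.9; three equal groups.

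**Assumptions:** 20 women per arm; two-sided 5%; 48-72 h correlation ρ of 0.5 or 0.7; the same group difference at 48 h as at 72 h; 10-30% missing at 72 h.

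**1. Complete rows.** If each reading is independently missing with probability m, the share of women with all k readings is (1 − m)^k.
- m = 5%: 0.95^5 = 77% for five times; 0.95^6 = 74% for six.
- m = 10%: 0.90^5 = 59%; 0.90^6 = 53%.

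**2. Power from lost numbers alone.** For a pairwise t test the noncentrality is (5/4.9) × √(n/2).
- n = 20: 1.02 × 3.16 = 3.23, power 88%.
- n = 16 (20% lost): 1.02 × 2.83 = 2.89, power 80%.
- n = 14 (30% lost): 1.02 × 2.65 = 2.70, power 74%.

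**3. The 72-hour contrast.** Suppose every woman below a common cut in 48-hour use leaves. In an arm whose standardised cut is c, the mean 72-hour value of those who remain rises by ρ × SD × λ, where λ = φ(c)/(1 − Φ(c)). The observed contrast is 5 − ρ × 4.9 × (λ_low − λ_high), where low and high are the lower-use and higher-use arms.

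With 20% missing overall, about 33% leave the lower-use arm and 7% the higher-use arm:
- λ_low = 0.362/0.67 = 0.541; λ_high = 0.134/0.93 = 0.144; difference 0.397.
- ρ = 0.5: 5 − 0.5 × 4.9 × 0.397 = 4.03 (simulation 4.05).
- ρ = 0.7: 5 − 0.7 × 4.9 × 0.397 = 3.64 (simulation 3.65).

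Large-sample simulation of the observed contrast (true value 5; ρ = 0.5 / 0.7):

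| Who is missing at 72 h | 10% | 20% | 30% |
|---|---|---|---|
| At random | 5.02 / 5.00 | 5.00 / 4.97 | 4.97 / 4.99 |
| Same rank rule within each arm | 5.00 / 4.97 | 5.03 / 4.99 | 5.00 / 4.99 |
| Low 48 h use, gradual common rule | 4.72 / 4.63 | 4.57 / 4.41 | 4.48 / 4.20 |
| Low 48 h use, sharp common cut | 4.39 / 4.13 | 4.05 / 3.65 | 3.80 / 3.30 |
| Low 72 h use (unseen), common cut | 3.74 / 3.79 | 3.08 / 3.09 | 2.58 / 2.59 |
| Lower-use arm leaves regardless of use; higher-use arm leaves only if 48 h use is low | 5.50 / 5.67 | 5.83 / 6.19 | 6.21 / 6.70 |

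A further run with low 48-hour users leaving first gave 4.2-4.8. A likelihood-type estimate that uses the earlier readings returns 4.97-5.03 in every row except the fifth. There it stays biased: 3.99 / 4.31, 3.42 / 3.83 and 2.95 / 3.43.

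**4. Size of the interaction test.** With three groups of 20 and five times, df are 2 × 4 = 8 and 57 × 4 = 228, and the 5% critical value is F = 1.98. When sphericity fails, the reference distribution has approximately both df multiplied by ε (ε = 1 under sphericity).
- ε = 0.81: P(F with 6.5 and 185 df > 1.98) = 6.5%.
- ε = 0.60: P(F with 4.8 and 137 df > 1.98) = 8.8%.

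Simulation (20,000 null trials per setting, 10-40 per arm) gave 4.7-5.2% when sphericity holds. Under serial correlation or unequal variances (ε from 0.81 to 0.49) it gave 6.3-9.3% with five times and 6.8-10.3% with six. With the Greenhouse-Geisser correction the range was 3.7-5.3%.

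**5. Effect on the final decision.** The two-stage rule was simulated under the null, assuming that the overall group effect is primary when the interaction is not significant (the plan does not say). Replacing the uncorrected interaction test by the Greenhouse-Geisser version lowered the final false-positive rate by only about 0.2-0.4 points.

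**The case against.** A reader might infer that early discharge will bias the 72-hour result toward no difference. The documents do not support that. They give no length of stay, discharge rule or missing rate, and the rationale says only that pain control can contribute to shorter stays. Co-investigators are assigned to collect the 72-hour readings, and the pilot reported 72-hour values in both arms. The table shows that the direction depends on the discharge mechanism.

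A reader might also infer that the 72-hour ANOVA discards every woman with any gap and rests on sphericity. It does neither: it is a between-group test at one time and loses only women without a 72-hour value. Row deletion in the repeated-measures part is the usual implementation, not something the plan states.

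Nor can one say that the interaction test does run above 5%. The plan promises to examine all assumptions, so the excess arises only if sphericity fails and nothing suitable is done. Unequal variance is not guaranteed by the unequal intervals. VAS is a score at a moment, and the pilot's Exparel opioid means (6.2, 5.5, 5.98, 5.23, 2.7 mg from 6 to 72 h) do not grow with interval length; variances are not reported.

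Finally, PCA opioid after the pump stops is arguably a known zero rather than a missing value. A mixed model that treats it as missing would estimate use that never occurred.

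All of this stands and limits the claim. It does not supply a missing-data method, and the remedies named still do not directly correct non-sphericity.

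**Conclusion.** The point holds in a conditional form and should be acted on.

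- **Missing data.** If low users leave first under a gradual common rule, a true 5 can appear as about 4.2-4.8 at 10-30% missing; a sharp cut would take it lower. Other mechanisms give no bias or bias away from zero. The 20 per arm, the correlations and the missing rates are assumptions.
- **Interaction test.** Uncorrected, it can run at about 6-10% under serial correlation or unequal variances. The consequence for the final conclusion is small, so this is the lesser half of the point.
- **72-hour ANOVA.** It needs neither sphericity nor complete rows. Its exposure is to missing 72-hour values only.

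A mixed model should not be read as a cure. It recovers the true contrast when missingness depends on recorded earlier use, but not when it depends on the unseen 72-hour value.

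**What to change.** 1. Replace the repeated-measures ANOVA with a mixed model for repeated measures: group, time, group by time and the timing-of-procedure stratum; unstructured within-patient covariance; Kenward-Roger degrees of freedom; every available reading included. Take the 72-hour group contrast from this model.
2. If ANOVA is kept for the interaction, report Greenhouse-Geisser-corrected p-values.
3. State whether PCA opioid after the pump stops, or after discharge, counts as zero or as missing. This defines what the 72-hour morphine contrast measures.
4. Add a sensitivity analysis for data not missing at random, since the main model does not cover that case.
5. Reconcile the number of time points (five in Post-operative Protocol, six in Planned Data Analysis), because the model needs one list.

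The cost is wording and slightly more analysis work. SAS, already named for the randomisation, can fit the model. The limit of the change is that the mixed model protects only when missingness depends on recorded earlier readings.

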Figure 2. Injecting bupivacaine into fascia and along incisional lines (C) prior to closure(Baxter et al).

Figure 3 A. Open abdomen prior to closure marking site of injection of either DepoBupivicaine or 0.25 % Bupivicaine (White Arrow) B. Using ultrasound probe in vivo C. Schematic of plane between the Internal Oblique and Transversus Abdominus

Post-operative Protocol

No short-acting analgesics, such as Fentanyl, will be given post-operatively. All patients will receive a narcotic intravenously through a patient-controlled analgesia pump programmed for demand-only mode (no basal rate). The patient-controlled anesthesia will be filled with morphine or hydromorphone (if patient sensitivity to morphine). Oral narcotics will be offered when the patient's diet is advanced as tolerated, typically post-operative day 1. Patients will be encouraged to ambulate on post-operative day 1. The continuous infusion pump catheters will be removed by the surgeon when the pump is empty. Drains will be removed when output is less than 30mL in a consecutive 24 hour period.

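### The one model in the analysis plan cannot test Aim 2's times to first ambulation, liquid and solid intake, and no rule covers a woman who has not reached a milestone

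*Combined protocol and SAP*

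**What the plan says.** Specific Aims, Aim 2, compares narcotic-related side effects "by documenting incidents of nausea and vomiting, time to first ambulation, and time to first liquid and solid oral intake". The Data collection section lists the milestones as single fields: "time to first ambulation, time to first liquid and solid intake post surgery". It has no field for a milestone not reached, for discharge, or for the end of observation.

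The Planned Data Analysis section states one method: "The data will be examined with an analysis of variance (ANOVA) procedure with repeated measures". The between factor is group with three levels and the within factor is time with six. If the group-by-time interaction is significant, the main analysis becomes the ANOVA at 72 hours. The only further provision is: "All assumptions of the test will be examined and data transformations or nonparametric methods used if indicated". No analysis is assigned to Aim 2 separately.

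Two statements bear on how many women might be unreached. Assessments end at 72 hours: "All measurements for variables were obtained at 6 hrs, 12 hrs, 24 hrs, 48 hrs, 72 hrs". The Post-operative Protocol expects early recovery: "Patients will be encouraged to ambulate on post-operative day 1". It also expects diet to be advanced typically on that day.

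**The concern.** A repeated-measures ANOVA compares a measurement taken several times on each patient. A time to first ambulation is measured once. It has no time profile, no group-by-time interaction and no value belonging to the 72-hour visit. Read literally, the plan offers no test for three of the four Aim 2 outcomes.

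The analyst must then improvise after seeing the data, and the main choice is what to do with a woman who had not walked, drunk or eaten when observation ended. She can be left out, given the last observed time, ranked last, or censored, and these choices can give different answers. The outcomes matter to the trial's argument: the pilot described under Significance reported that the Exparel group was walking, drinking and eating earlier than the On-Q group, so this trial would be expected to test that difference.

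**Working it through.** **Fit of model to outcome.** This step needs no assumptions.

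- VAS and opioid use have several values per patient, so the group-by-time model can be fitted.
- Nausea and vomiting incidents can be tabulated per interval, so a repeated-measures layout is at least possible.
- Times to first ambulation, liquid and solid intake have one value per patient. The within factor does not exist, and neither the interaction test nor the 72-hour ANOVA can be computed.

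**Size of the effect of handling.** The documents give no milestone times, no unreached share and no sample size, so there is no plan figure to reproduce. Everything below is illustrative, tested at the 5% level. Because the repeated-measures model cannot be run, the comparator is a one-way ANOVA on the single times.

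*Setting A, many unreached.* Assume exponential times, medians 18, 36 and 36 h, 20 per group, cutoff 72 h.

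- Unreached share = 2^(−72/median): 2^(−4) = 6.25% and 2^(−2) = 25%.
- Mean = median/ln 2: 26.0 h and 51.9 h, a difference of 26 h.
- Mean restricted to 72 h = mean × (1 − unreached share): 26.0 × 0.9375 = 24.3 h and 51.9 × 0.75 = 38.9 h, a difference of 14.6 h.
- Mean among reached women = mean − 72 × share/(1 − share): 26.0 − 4.8 = 21.2 h and 51.9 − 24.0 = 27.9 h, a difference of about 6.8 h (6.6 h in simulation).

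The fair yardstick for data ending at 72 h is 14.6 h, not 26 h. Simulated power, in runs of 1,500 trials, was 16% to 20% for ANOVA on reached times only, 49% for ANOVA with unreached women set to 72 h, 47% for Kruskal-Wallis with them ranked last, and 54% to 57% for log-rank.

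*Setting B, few unreached.* Assume lognormal times, medians 18, 27 and 27 h. With log-SD 0.4, under 1% are unreached, and power was 86% for ANOVA on reached times and 87% to 88% for log-rank. With log-SD 0.5, about 2.5% are unreached in the slower arms, and power was 65% against 70%.

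*Setting C, a gradient.* Assume lognormal times, log-SD 0.6, 16 per group, common 72 h cutoff, 1,000 trials each.

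| Unreached by arm | ANOVA, reached only | ANOVA, set to 72 h | Kruskal-Wallis, ranked last | Log-rank |
|---|---|---|---|---|
| about 2/5/10% | 0.46 | 0.55 | 0.57 | 0.56 |
| about 7/17/29% | 0.33 | 0.58 | 0.56 | 0.55 |
| about 21/39/55% | 0.18 | 0.55 | 0.54 | 0.54 |

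*Setting D, no true difference, observation ending at different times.* Same lognormal model, median 40 h in every arm, observation ending at 36, 54 and 72 h by arm. Rejection rates were 0.36 (reached only), 0.50 (set to last time), 0.18 (Kruskal-Wallis, ranked last) and 0.04 (log-rank). The two ANOVAs showed a false difference of about 12 h. With a common cutoff and no true difference, all methods rejected in about 0.05 to 0.07 of trials.

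**The case against.** A reader might infer that Aim 2 would be biased toward no difference. The documents do not support that. The plan never says unreached women are excluded; it is silent. The milestone fields carry no 72-hour cap, so a later time could be entered as it occurred. The only evidence on timing, the day-1 expectations for walking and diet, suggests few women would be unreached at 72 hours, and the loss is then small (Setting B). The large gap in Setting A comes mainly from assuming that unreached women are dropped: setting them to 72 h recovers most of the power. If observation ends at different times by arm, the error can run the other way and create a difference (Setting D). This part of the objection stands in full.

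The assumption-check clause also permits nonparametric methods, and a rank test with unreached women placed last lost essentially nothing against log-rank in Setting C. That is fair, but the clause does not name the test or say where such women are ranked. It is triggered by checking the assumptions of a model that cannot be fitted to these outcomes, so it does not close the gap.

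A reader might also extend the point to nausea and vomiting. Those incidents can be tabulated by interval, and the clause already covers non-normal data. A count model there would be mostly a preference.

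Finally, these are not the primary endpoints, which limits the impact.

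**Conclusion.** The point holds in a narrow form. The stated model cannot test the three times to first event in Aim 2, and the plan has no rule for a woman who has not reached a milestone by discharge or 72 hours. Both follow from the text without assumptions.

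The numerical consequence is not established. It ranges from negligible (86% against 88% power with under 1% unreached) to large (about 18% against 56% with 25% unreached in two arms), and every input to those figures is assumed. The protocol's own expectations favour the small end. The direction is open, because it depends on the handling chosen and on whether observation ends at the same time in every arm. The Rationale section links effective pain control to shorter stays, so unequal observation is possible, though not shown. This is a minor but real gap in a secondary aim.

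**What to change.** For the three milestone times, replace the repeated-measures ANOVA with Kaplan-Meier curves and a log-rank test stratified by procedure timing (the randomization stratum), censoring at the last observation, whether discharge or 72 hours. This assumes that, within an arm, the end of observation is unrelated to how soon the milestone would have been reached. If every woman is followed to the same cutoff, a Kruskal-Wallis test with unreached women ranked last is an acceptable alternative.

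Add to Data collection the actual clock time of each milestone and the last observation time. The present wording ties measurements to five scheduled times and leaves unclear whether exact times are captured. Keep the repeated-measures model for VAS and opioid use; its six time levels against five listed times should be reconciled separately.

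The cost is two or three sentences in the analysis section, one added data field, and slightly more analysis work.
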